7.2 Vital Signs

A summary (table) of blood pressure (systolic and diastolic) will be reported at Baseline/Visit 1, immediately pre dose (Visit 1), post dose (Visit 1), Visit 2 (Post EVT) and at Visit 3 (Day 2/3). Absolute values and changes from Baseline (Visit 1) to post dose (Visit 1), Visit 2 (Post EVT) and at Visit 3 (Day 2/3) will be summarized descriptively.

A summary (table) of heart rate will be reported at Baseline/Visit 1 (pre-dose), Visit 2 (Post EVT) and at Visit 3 (Day 2/3). Absolute values and changes from pre-dose to Post EVT and Day 2 will be summarized descriptively.

A summary (table) of temperature will be reported Baseline/Visit 1 (pre-dose), Visit 2 (Post EVT) and at Visit 3 (Day 2/3). Absolute values and changes from pre-dose to Post EVT and Day 2 will be summarized descriptively.

A listing of all vital signs will be provided.

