- 4. At baseline estimated or actual weight will be collected. If an estimated weight was collected at baseline, actual weight should be collected as soon as feasible and prior to discharge.
- 5. Vital signs (BP, HR only) will be recorded immediately before and after completion of the study drug infusion, temperature will be collected at baseline only if standard of care.
- 6. Historical (pre-stroke) mRS score can be collected at any time.
- 7. MRI head may be supplanted by an NCCT head if MR is unavailable or contraindicated.
- 8. Blood should be drawn at baseline, but results are not required prior to randomization. Results from primary hospital (within 8 hours) are accepted.
- 9. If the participant is female and is of childbearing potential a pregnancy test (urine or serum point-of-care pregnancy test) must be completed and the result must be negative; this is the only mandatory laboratory test prior to randomization.
- 10. PK samples will be collected from up to 100 participants: pre-dose and at 10, 20, 30 and 60 min after the start of study drug administration.

d = days; h = hours

Contact	V7
	1-Year Follow up
Day	Day 365
Window	(±30 d)
Mortality	X
EQ-5D-5L	X
mRS	X
Barthel Index	Х

Table 1-2: Schedule of Activities: 1-Year Follow Up Telemedicine or Telephone Contact

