The results of the safety analysis from the ESCAPE-NA1 trial indicate that nerinetide was well tolerated when given as a single IV dose of 2.6 mg/kg with most adverse events occurring with a similar frequency in the drug and placebo groups. The only exception to that was an increase in serous hypotension immediately (within 2 hours) following the administration of nerinetide (6 SAEs in nerinetide vs. 0 in placebo). These cases were reported resolved within 2 days. There were no other differences in other important safety outcomes observed. When nerinetide is administered without alteplase there were fewer deaths and a fewer number of neurological serious adverse events (including stroke in evolution, ischemic stroke and hemorrhagic transformation). When nerinetide is administered with alteplase there were no differences in important safety outcomes observed.

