8.2.1 Vital Signs

Blood pressure and heart rate will be taken at Baseline (pre-dose), at the completion of drug infusion and Day 2. Results taken from standard of care assessment/timepoints may be used. Temperature will be taken at baseline (if available per standard of care) and Day 2. Clinically significant findings post-dose will be reported as AEs.

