9.3.3 Analyses of Safety

All safety analyses will be performed on the Safety Population. The main analyses will be frequency of SAEs and 90-day mortality.

Endpoint	Statistical Analysis Methods
Serious Adverse Events	The frequency of SAEs will be summarized using the Medical Dictionary for Regulatory Activities (MedDRA) Version 23.1.
SAEs leading to death	The frequency of fatal SAEs will be summarized using the Medical Dictionary for Regulatory Activities (MedDRA) Version 23.1.
Adverse Events	The frequency of AEs will be summarized using the Medical Dictionary for Regulatory Activities (MedDRA) Version 23.1.
Vital Signs	Absolute values and changes for vital signs from pre-dose to Day 2 will be documented. The maximum deviation of BP from Baseline between drug and placebo control groups (systolic and diastolic) to Day 2 will be analyzed.
Lab Safety	Absolute values for laboratory results will be summarized descriptively.
Prior and Concomitant Medications	Prior and concomitant medications will be summarized using the WHO Drug Dictionary.

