1.8 Definitions

Baseline: A subject's baseline value for a given endpoint or parameter is defined as his/her latest measurement taken prior to study drug administration.

Prior and Concomitant Medications: Prior medications are defined as those taken within 24 hours prior to randomization. Concomitant medications are defined as those taken during study drug administration or after study drug has been administered through to Day 6 (or discharge). All prior and all concomitant medications will be recorded on the electronic case report form.

Randomization: The time of randomization is defined as the time randomization occurred on the central server and this time is considered time zero for the study. All time windows are calculated from the time of randomization.

Study Day: Day 1 is the date of randomization. As the study drug is intended to be administered as soon as possible after randomization (i.e., 15 minutes), this will also be the day of treatment initiation date. Study day is calculated relative to Day 1.

Treatment-Emergent Adverse Event: All AEs will be collected from the start of study drug administration until Day 30. All SAEs will be collected from the start of study drug administration until Day 90. A treatment-emergent adverse event (TEAE) is one that first occurs or worsens in severity or frequency after study drug administration has begun through to and including the Day 30. SAEs are collected through the last study visit. Those AEs that start at the same time and date as the study drug administration and those that first occur or worsen after the start of study drug administration will be considered TEAEs.

AEs with partial or missing dates will be handled as follows:

- If the start day and/or month of the AE is missing the AE will be considered treatmentemergent.
- If the start date is completely missing then the AE will be considered treatment-emergent.

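### SAP 7.2 omits the between-arm analysis of maximum blood-pressure deviation that protocol 9.3.3 says will be done, and leaves the collected end-of-infusion heart rate out of its table

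*Combined protocol and SAP*

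**What the plan says.** Protocol 9.3.3, in the vital-signs row of its table: "The maximum deviation of BP from Baseline between drug and placebo control groups (systolic and diastolic) to Day 2 will be analyzed". No derivation, test or estimate is given. The synopsis also lists post-dose vital signs to Day 2 as an additional safety outcome.

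SAP 7.2 gives BP rows at Baseline/Visit 1, then "immediately pre dose (Visit 1), post dose (Visit 1), Visit 2 (Post EVT) and at Visit 3 (Day 2/3"). It summarises descriptively "Absolute values and changes from Baseline (Visit 1) to post dose (Visit 1), Visit 2 (Post EVT) and at Visit 3 (Day 2/3"). No maximum deviation and no comparison between arms appears. For heart rate: "A summary (table) of heart rate will be reported at Baseline/Visit 1 (pre-dose), Visit 2 (Post EVT) and at Visit 3 (Day 2/3").

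Collection is wider than that heart-rate table. Footnote 5 of protocol Table 1-1, repeated under SAP Table 2, says: "Vital signs (BP, HR only) will be recorded immediately before and after completion of the study drug infusion". Protocol 8.2.1 says: "Blood pressure and heart rate will be taken at Baseline (pre-dose), at the completion of drug infusion and Day 2". Section 8.2.1 does not mention the post-EVT reading that Table 1-1 and SAP 7.2 both contain.

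On the reference value, SAP 1.8 says: "A subject's baseline value for a given endpoint or parameter is defined as his/her latest measurement taken prior to study drug administration".

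On the risk, protocol 2.1.5 reports from the previous trial "an increase in serous hypotension immediately (within 2 hours) following the administration of nerinetide (6 SAEs in nerinetide vs. 0 in placebo"), as the only exception to broadly similar adverse-event frequencies. Protocol 2.3.1 lists transient hypotension from a transient rise in histamine as a major possible risk.

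Protocol 9.3 provides that, where protocol and SAP are inconsistent, the analysis follows the SAP.

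**The concern.** A safety analysis announced in the protocol has no counterpart in the document that governs the analysis, and it concerns the main drug risk identified so far. The stated mechanism is a short fall in pressure, probably in a minority of participants. Summaries by time point are weak for that pattern: a large fall in a few people hardly moves a mean, and nothing in SAP 7.2 counts how many participants had one or estimates a difference between arms.

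Two smaller gaps touch the same data. Heart rate at the end of infusion, the reading closest to the drug effect, is collected but not tabulated. And the BP table separates a Baseline/Visit 1 row from an immediately pre-dose row, then takes change from Baseline (Visit 1), so the reference for the fall is unclear although SAP 1.8 would make it the latest pre-dose value.

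**Working it through.** The core of the point is a comparison of texts.

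| Item | Protocol | SAP |
|---|---|---|
| Maximum BP deviation, between arms, to Day 2 | 9.3.3: will be analysed | 7.2: absent |
| BP at end of infusion | 8.2.1 and Table 1-1 footnote 5: collected | 7.2: tabulated, with change |
| Heart rate at end of infusion | 8.2.1 and Table 1-1 footnote 5: collected | Table 2 footnote 5: collected; 7.2: not tabulated |
| Post-EVT reading | Table 1-1: yes; 8.2.1: not mentioned | Table 2 and 7.2: yes |
| Reference for BP change | 9.3.3: baseline | 1.8: latest pre-dose value; 7.2: Baseline (Visit 1), listed apart from immediately pre-dose |

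**Number of readings behind a maximum.** Table 1-1 gives three scheduled post-dose BP readings (end of infusion, post-EVT, Day 2/3). Section 8.2.1 gives two. Protocol 6.8.1.1 expects dosing to finish before the endovascular procedure does. If the post-EVT visit is about two hours after the procedure, it falls more than two hours after dosing, and only the end-of-infusion reading lies in the two-hour risk period.

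**The previous signal.** With six events and 1:1 allocation, the chance that all six fall on nerinetide is 0.5^6 = 0.0156 one-sided, or 2 × 0.0156 = 0.031 two-sided. This makes no allowance for the number of event terms examined.

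**What a mean shows.** Assumptions, none from the documents: 3% of nerinetide participants have a 50 mmHg fall at a reading, and the SD of the change is 20 to 30 mmHg. Arm size is 850/2 = 425 from the protocol; the SAP still plans 680 to 1,020 participants.

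- Mean shift = 0.03 × 50 = 1.5 mmHg.
- SE = SD × sqrt(2/425): 1.37 at SD 20, 1.71 at SD 25, 2.06 at SD 30.
- z = 1.5/SE: 1.09, 0.87 and 0.73.

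A second set of assumptions (40 mmHg fall, SD 15 to 25, two-sided 0.05) gives these powers for a comparison of means:

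| Share affected | Mean shift | Power |
|---|---|---|
| 2% | 0.8 mmHg | 7% to 12% |
| 5% | 2.0 mmHg | 21% to 49% |
| 10% | 4.0 mmHg | 65% to 97% |

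**What a count shows.** With the same 3% added to an assumed background of large falls:

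- Background 2%, so 5% vs 2%: SE = sqrt((0.05 × 0.95 + 0.02 × 0.98)/425) = 0.0126; z = 0.03/0.0126 = 2.4.
- Background 10%, so 13% vs 10%: SE = sqrt((0.13 × 0.87 + 0.10 × 0.90)/425) = 0.0219; z = 0.03/0.0219 = 1.4.

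A mean of maximum falls would be diluted in the same way as a mean at one reading: 3% of 50 mmHg is still at most 1.5 mmHg. Restoring the protocol's sentence literally, as a comparison of means, would therefore not be enough. The counts carry the information.

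**The case against.** The strongest reply is that the SAP already has a dedicated route for this risk. SAP 7.1 tabulates by arm, and lists, events of special interest with onset 0-120 minutes after the end of infusion, and SAP Table A-2 is a list of hypotension and blood-pressure terms. Protocol 6.8.1.2 requires hypotension to be recorded as an AE when systolic pressure is below 80 mmHg or the physician judges the fall clinically relevant. Serious events are tabulated by preferred term. SAP 4.1 includes minimum and maximum in continuous summaries by default, SAP 7.2 keeps the post-dose BP change, and all vital signs are listed. The 6 vs 0 signal was itself a count of SAEs, and that route is intact.

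This stands. A reader might infer from SAP 7.2 alone that acute hypotension would be hidden in visit means; the documents do not support that.

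A reader might also infer that the sponsor removed the analysis. That cannot be shown. SAP 2.0 follows Protocol V5.0 of November 2021, which is not available, while the protocol under review cites 2022 software. The evidence supports an omission only.

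It can further be argued that silence in the SAP is not an inconsistency, so the protocol's sentence survives. Even then, protocol 9.3 leaves the technical detail to the SAP, and neither document defines the analysis.

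What the reply does not cover is independence from reporting. A fall from, say, 170 to 120 mmHg is 50 mmHg but stays above 80, so whether it becomes an AE depends on judgement. The minimum change shows the single largest fall per arm at each reading, not how many participants fell or by how much the arms differ. A listing gives no comparison.

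On the baseline, SAP 1.8 can be read as settling the matter, which makes that part a labelling ambiguity.

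**Conclusion.** The point holds as an omission with a limited consequence. One protocol-stated safety analysis and one collected heart-rate reading are missing from the governing plan. The primary efficacy analysis is untouched, and hypotension that is reported as an event will be counted by arm.

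The loss is a between-arm check on measured pressures that does not pass through investigator judgement, on a risk the protocol itself singles out. It would use data already collected, so this is more than missing detail and should be corrected.

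The omission itself rests on the text and needs no assumption. The figures for dilution and for counts are illustrations on assumed frequencies, falls, SDs and backgrounds. They show that a mean can miss a rare large fall and that a count can do better, but not that a count would always be conclusive: at a 10% background it gives z of only 1.4.

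**What to change.** In SAP 7.2:

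1. Add each participant's maximum systolic and maximum diastolic fall from the immediately pre-dose value to Day 2. Report the between-arm difference with a 95% CI, and the number of participants per arm by size of fall, with categories fixed before unblinding.
2. State that all BP changes are taken from the immediately pre-dose value, which is the SAP 1.8 baseline.
3. Add end-of-infusion heart rate, and its change, to the heart-rate table.

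Across the documents:

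4. Reconcile the reading times in protocol 8.2.1 with Table 1-1 and SAP 7.2.

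The cost is SAP wording and a few table shells, with no new procedure or data. The limitation should be reported with the result: the maximum rests on at most three scheduled post-dose readings (two under 8.2.1) and can miss a nadir between them. A CRF field for the lowest pressure in the two hours after infusion, taken from routine charts, would lessen this. It is optional, because it adds data entry and charting frequency will vary between sites.

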7.3 Laboratory Results

A summary (table) of complete blood count (Platelets, hematocrit and hemoglobin), electrolytes (sodium, potassium and chloride) and chemistry (serum creatinine and serum glucose) will be reported at Baseline and Day 2.

Absolute values and change from baseline values for laboratory results will be summarized descriptively. Inferential statistics (ie, p-values or CI) will not be provided for these data.

A listing of all laboratory results as well as abnormal lab values post-dose will be provided.

7.4 Concomitant Medications

All concomitant medications collected on the Case Report Form with a start date prior to the date of Visit 4 (Visit will occur at Day 6 or hospital discharge if prior to Day 6) will be summarized by ATC Level 1 and Preferred Term within treatment group as well as listed in by-treatment by-subject listings.

8 INTERIM ANALYSIS

There will be an unblinded interim analysis and sample size re-estimation (SSRE) conducted in this trial when approximately 510 participants (75% information based on initial sample size) completed their 90-day study visit (that is when 510 participants have either completed Day 90 visit or discontinued from the study prior to Day 90 visit).

The interim analysis will be conducted by the unblinded statistician in the independent Statistical Group. An IDMC will review the interim efficacy and SSRE results.

Depending on enrollment rates, it may be necessary to perform the interim analysis before 75% information to ensure sample size re-estimation is completed before the study has been fully enrolled.

8.1 Interim Efficacy Analysis

There will be an interim efficacy analysis for unblinded sample size re-estimation in this trial. It will be conducted by the unblinded statistician in the Independent Statistical Group.

The interim efficacy analysis will be performed after approximately 510 participants have complete the Day 90 follow-up, at 75% information on the primary endpoint. The interim efficacy analysis will be conducted on the ITT population, following the same methods as the study final analysis described in Table 5 below.

Endpoint		Analysis	
Primary	Day-90 mRS Responder (≤2 vs. >2)	Adjusted log-binomial regression model, ITT, SI	
Secondary	Day-90 Mortality	Adjusted log-binomial regression model, ITT Missing data imputed based on Day 30 status	
	Worsening of Stroke	Adjusted log-binomial regression model, ITT, Missing data imputed based on Day 30 status	
	Day-90 mRS shift (Ordinal)	POM, ITT, SI	
	Day-90 NIHSS Responder (≤2 vs. >2)	Adjusted log-binomial regression model, ITT, LOCF	

Table 5: Summary of Interim Efficacy Analyses

The planned initial sample size is of 680 evaluable participants randomized 1:1, allowing for a single interim analysis at 75% information (when about 510 patients have primary endpoint assessments) with O'Brien-Fleming alpha-spending function stopping boundary for overwhelming efficacy as well as the possibility of sample size re-estimation based on conditional power at the same interim look using the Chen-DeMets-Lan approach⁷ for unblinded sample size re-estimation. The trial-wise alpha (FWER) will be controlled at pivotal, 1-sided 0.025 level via primary analysis using standard group sequential Wald test for comparison of 2 independent proportions^{7,18} (EaST v6.5 2020), in spite of the sample size re-estimation, by the "promising zone" method using the Chen-DeMets-Lan approach^{1.} The cumulative alpha spent at the interim analysis is 0.01 and final analysis 0.025, 1-sided; the stopping boundaries on the Z scale are 2.34 (interim) and 2.012 (final) and on the p-value scale 0.01 (interim) and 0.022 (final), all on the assumption that the interim is conducted at 75% information (EaST v6.5, 2020). If the interim analysis is conducted at a different time point other than when 75%

information available, the type I error and the efficacy boundary for the interim and final analysis will be adjusted accordingly using nQuery Advisor[®].

Power calculations for the unblinded sample size re-estimation design were run via simulation under the assumption of 2% probability of dropout during the trial (across both arms) using the Chen-DeMets-Lan approach¹ for unblinded sample size re-estimation with a maximum sample size of 1020 randomized (sample size re-estimation inflation factor 1.5) and inflation based on conditional power promising zone between 50% and 80% based on the observed trend at the interim and using a Wald statistic (using a sample size increase rule to be specified in the IDMC Charter to prevent back-calculation of interim effect sizes).

The IDMC may recommend stopping for overwhelming efficacy at the interim analysis if the test statistic crosses the O-F boundary. Additionally, the IDMC may recommend a sample size modification for the trial per the pre-specified re-estimation criteria which are outlined in the IDMC Charter, based on the interim results provided by the Independent Reporting Statistician/Independent Statistical Center to the IDMC. However, notwithstanding the O-F superiority critical p-value of 0.01 for stopping (boundary value) at the interim analysis of the primary efficacy outcome, the IDMC will be instructed to make a recommendation on stopping per their own review of all data, and also, in support of their recommendation, to report to the Sponsor/Steering Committee whether or not the superiority boundary was crossed and how the study sample size should be adjusted after the interim analyses. The IDMC Charter will provide further details on the rationale for, and how, these recommendations will be communicated.

The following summary tables and analyses will be performed at the interim analysis (also see Table 5) and provided to the IDMC in support of consideration of stopping for overwhelming efficacy at the interim analysis:

- Subject disposition (e.g., number completed Day 90 visits) by treatment group
- Subject demographics and baseline characteristics (as described in Section 5.5) by treatment group
- Primary efficacy endpoint:
 - Proportion of participants with independent functioning on the modified Rankin Scale (mRS), as defined by a score of 0-2 (mRS responder) at Day 90
- Secondary efficacy endpoints:
 - Mortality rate over the 90-day study period
 - Proportion of participants with worsening of stroke over the 90-day study period
 - Shift in mRS categories at Day 90 (mRS shift analysis)
 - Proportion of participants with a score of 0-2 on the NIHSS at Day 90

By-subject data listings will also be provided to support the interim tables.

The unblinded statistician in the Independent Statistical Group will also perform the conditional power calculation and sample size re-estimation by using nQuery Advisor[®] (Interim Monitoring and Unblinded Sample Size Re-estimation Module). The sample size increase rules will be provided to the unblinded statistician directly by the external regulatory statistician as per IDMC Charter, and will not be shared with any blinded study team members prior to database lock. The nQuery results, including the Wald test statistics and conditional power based on the treatment

effects at interim, boundary values per correct information time of interim analysis, sample size re-estimation rules, the re-estimated new sample size (if applicable) and the conditional power based on the new sample size will be provided to IDMC in a format (e.g. executive summary in a report or presentation slides) as deemed appropriate by the unblinded statistician.

8.2 Safety Analysis

The Independent Statistical Group will generate safety reports, which will include cumulative summary statistics; subject status in the study (e.g., number completed Day 90 visits); baseline characteristics; safety data, including adverse events (AEs) and serious adverse events (SAEs) by AE code, and discontinuations due to AEs. The IDMC may recommend stopping for safety at the interim analysis.

The following safety summaries (tables) will be provided to the IDMC:

- Overview of Adverse Events
- TEAEs (with a start date 0-30 days) by MedDRA SOC and preferred term
- Serious TEAEs (with start date 0-90 days) by MedDRA SOC and by preferred term
- All TEAEs resulting in death by MedDRA SOC and by preferred term
- All TEAEs resulting in discontinuation of treatment, by MedDRA SOC and by preferred term

The following listings of AE occurrences will be provided:

- All AEs by MedDRA SOC and by preferred term
- All SAEs by MedDRA SOC and by preferred term
- All AEs leading to death by MedDRA SOC and by preferred term

